Title of Study: Toileting at Night in Older Adults: Light to Maximize Balance, Minimize Insomnia

NCT number: NCT01350505

Date of document: 9/26/18

Initial protocol

Study Procedures

Subjects will be initially phone screened before being asked to come to the lab for a screening visit. By including the phone screen, we have found that our failure rate during the screening visit is relatively low (around 20%). Our previous experience indicates that relatively few of the randomized subjects will be disempaneled. Subjects will be randomized after passing their lab screening visit; subjects who are disempaneled will be replaced. Subjects will be block randomized in three groups of nine (three in each condition), with drop-outs replaced. In-person screening will consist of discussion and signing of the consent form and completion of the following forms or tests: demographics, medication/health log, Owl and Lark Questionnaire ('morningness'/'eveningness'), Ishihara Color Plate (color blindness), Mini Mental State Exam (dementia), Pittsburgh Sleep Quality Index (sleep disorders), Geriatric Depression Scale, AUDIT (alcoholism), Balance Self-efficacy Scale (self-assessed balance), Nocturia, Nocturnal Enuresis and Sleep-interruption Questionnaire, Octopus 900 (peripheral vision), and ETDRS (visual acuity).

For one week prior to entry into the laboratory, subjects will be required to maintain a regular sleep-wake cycle. The purpose of this schedule is to ensure that subjects have adequate sleep time (i.e., are not significantly sleep deprived) before coming into the laboratory and to regularize exposure to light and dark which should, in theory, help to maximize the amplitude of the oscillation of the circadian pacemaker and to stabilize the phase angle between the circadian pacemaker and the sleep schedule. A regular sleep-wake cycle is defined for these purposes as having nocturnal time in bed being between 7 and 9 hours and going to bed and arising within 30 minutes of target bed and wake times. The prospective timing of sleep during this one-week period will be determined by consensus between the subject and research personnel. Compliance with the schedule will be determined through use of wrist actigraphy (Actiwatch 2, Philips Respironics) and concomitant sleep logs. Wrist actigraphy is a validated, low burden technique for estimating the timing of sleep and wake. The Actiwatch 2 is a small device (16 g) about the size of a standard wrist watch that collects data on three dimensional movement using a piezoelectric accelerometer (sample rate = 32 Hz, sensitivity = 0.025 G). It includes a silicon photodiode for detection of ambient illumination ($\nu\lambda$ filtration for photopic sensitivity, 5-100,000 lux range) and an event marker that the subject will be instructed to press when entering and exiting bed. It has a rechargeable lithium battery and will be set to collect data as the integrated movement occurring during 30 second intervals. On-board memory with these settings is sufficient for 15 days of recording. The Actiwatch 2 is waterproof and subjects will be instructed to wear the Actiwatch continuously, including during bathing. Using the automated sleep scoring software that comes bundled with the Actiwatch 2 (Actiware 5, Philips Respironics), the actigraph illuminance data, and the self-reported sleep diaries, at-home sleep patterns can be accurately assessed. Upon entry to the laboratory at the end of the one-week phase/amplitude stabilization protocol, compliance with the sleep schedule will be verified. Subjects who were unable to maintain the required sleep schedule will be disempaneled or rescheduled. Otherwise, the average bed and wake times will be calculated (removing up to two variant times) and the midpoint calculated. This will be the midpoint of the subject's 8 hour in-lab sleep opportunity in the dark.

After the one-week, at-home protocol, subjects will come to the laboratory three hours before their scheduled bed time. Following confirmation of their at-home sleep schedule, subjects will produce a

urine and saliva sample. Urine will be tested for the presence of common illegal drugs (cocaine, tetrahydrocannabinol, methamphetamine; DrugCheck3, Express Diagnostics; result in 5 minutes) and saliva will be tested for the presence of alcohol (Chematics, Alco-Screen 02; result in 4 minutes). The presence of illegal drugs or alcohol (>0.02% blood alcohol content) will result in dispanelment. Other than indicating in the medical record that the subject was dispaneled for cause, no other record of the drug and alcohol tests will be kept. Cleared subjects will be brought to the Stanford University/VA Palo Alto Health Care System Sleep and Circadian Translational Research Laboratory (SCTRL). During their entire stay at the SCTRL, subjects will remain in a time isolation suite (no windows, no clocks or other time cues, *en suite* bathroom, regulated temperature of 70 °F, all lighting controlled from outside the suite). Upon entry into the SCTRL until the subject leaves the next morning, illuminance is kept at normal room lighting (~150 lux in any angle of gaze) except during hours of scheduled darkness (<0.03 lux) and the 13-minute experimental light stimulus. In the SCTRL, the floors are white and the walls are painted with a white, titanium dioxide-based paint that increases luminosity and ensures a relatively even illuminance across the room.

After entry into the SCTRL, subjects will have a baseline testing sequence: Stanford Sleepiness Scale (subjective sleepiness), visual acuity testing, peripheral vision testing, mobile balance testing (walking on a specialized, pressure-sensing walkway), Karolinska Drowsiness Task (EEG monitoring of drowsiness), mobile balance testing, auditory version of the Psychomotor Vigilance Test (objective alertness), a five minute break while seated, and the sequence repeated. During this testing, brain wave activity (electroencephalogram, electromyogram) and eye movements (wireless eye tracking) will be monitored. This will serve as a baseline test to account for interindividual variability. Subjects will go to sleep at their habitual bed time (calculation described above).

After 2 hours in darkness subjects, will be awakened by the technician into one of the three experimental lighting conditions (dim white light, room light, dim orange light) and be kept awake for 13 minutes. Subjects will be tested with the same sequence as at baseline. Following the 13-minute experimental light exposure, subjects will be allowed to sleep in darkness until their typical wake time. Upon awakening, subjects will be given a subjective test of alertness (Stanford Sleepiness Scale), an objective test of alertness (Psychomotor Vigilance Test), and a questionnaire regarding the previous night of sleep (Groningen Sleep Quality Questionnaire). They will then be provided a standard hospital breakfast and discharged.

Exposure to the experimental light will always start two hours after habitual bedtime and last 13-minutes. The first two conditions, very dim white light (0.5 lux, low mesopic range) and dim white room light (5 lux). The illuminance will be confirmed with a photometer (IL1700, International Light, Peabody MA). The orange light condition will be produced by filtering the fluorescent lamps with an acrylic filter (Roscolux #19 "Fire", Roscolux, Glendale CA) so as to produce 1×10^{13} photons \cdot cm $^{-2}$ \cdot s $^{-1}$ or an equivalent LED light.

As a follow-up to this original protocol, subjects who completed all three of the visits previously described, and who indicated a willingness to be recontacted, will be asked to sign a new consent form and participate in a single overnight visit (with preceding at-home sleep monitoring) identical to the described, except that they will be awoken into normal room light (150 lux).

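### Completed nights of replaced subjects would ordinarily fall out of the repeated-measures ANOVA, and the SAP does not say that the collected baseline is used for gait; a mixed model would use both

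*Protocol*

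**What the plan says.** The Protocol's Study Procedures state the replacement rule twice: "Subjects will be randomized after passing their lab screening visit; subjects who are disempaneled will be replaced", and "Subjects will be block randomized in three groups of nine (three in each condition), with drop-outs replaced". Losses are expected to be rare: "Our previous experience indicates that relatively few of the randomized subjects will be disempaneled". The same section gives two routes of removal after randomisation, both checked on arrival at the laboratory. One is the at-home sleep schedule: "Subjects who were unable to maintain the required sleep schedule will be disempaneled or rescheduled". The other is the drug and alcohol test: "The presence of illegal drugs or alcohol (>0.02% blood alcohol content) will result in dispanelment".

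On the pre-sleep test sequence, which includes walking and EEG, the Protocol says "This will serve as a baseline test to account for interindividual variability".

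The SAP's Initial analysis plan names two primary outcomes, the variability of walking speed between strides and the change in EEG delta power. It tests them with repeated-measures ANOVA and post hoc t-tests. Neither document defines an analysis population, gives a rule for partly observed subjects, or says whether a replaced subject's completed nights are kept. The SAP does not mention the baseline for gait.

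**The concern.** The point depends on each subject attending three experimental nights. The Protocol's follow-up paragraph, which refers to people who finished three visits, and the SAP's choice of a repeated-measures method support this. The allocation sentence, with three per condition in each group of nine, leaves it open.

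On the three-night reading a subject can leave after one or two nights. A classical repeated-measures ANOVA ordinarily needs every condition for every subject, so that subject's nights would not enter. A paired t-test needs only two nights, so the post hoc comparisons could rest on more subjects than the ANOVA they follow. The plan does not settle this, and the choice could be made after the data are seen.

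Precision is also at stake. The plan as written would ordinarily set aside valid measurements of both primary outcomes. For gait it does not commit to using a baseline collected to account for differences between people.

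**Working it through.** The documents give no loss rate, standard deviation or power calculation, so there is no stated figure to reproduce.

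**Inputs**
- From the Protocol: 3 groups × 9 = 27 completers.
- Assumed: 1 or 3 subjects lost after one or two nights; within-subject SD σw = 0.7; between-subject SD σb from 0.7 to 2.0. Only the ratio of the SDs matters.
- Method: generalised least squares with known variances. The standard error (SE) of a light contrast is compared with and without the lost subjects' nights, averaged over the three pairwise contrasts.

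**1. What the named method does with incomplete subjects.** Data were simulated for 27 complete subjects plus three with two nights each. A standard repeated-measures ANOVA routine refused the data as unbalanced. It ran only on the 27, with (3−1) = 2 and (27−1)(3−1) = 52 degrees of freedom. A random-intercept mixed model used all 27×3 + 3×2 = 87 nights.

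**2. One lost subject with one night (no visit term).** Let ρ = σb²/(σb²+σw²). The variance of the two contrasts involving that night's light falls by the fraction (1−ρ)/56; the third contrast is unchanged.
- σb = 0.7: 0.500/56 = 0.893%, so SE −0.447% on two pairs; average 2×0.447/3 = 0.30%.
- σb = 2.0: 0.109/56 = 0.195%, so SE −0.098% on two pairs; average 0.065%.

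**3. One lost subject with two nights (no visit term).** For the pair observed, SE falls by 1−√(27/28) = 1.802%. For each other pair the variance falls by 1/112 + σw²/[224(σb²+σw²/2)].
- σb = 0.7: 0.008929 + 0.002976 = 0.011905, SE −0.597%; average (1.802+0.597+0.597)/3 = 1.00%.
- σb = 2.0: 0.008929 + 0.000515 = 0.009444, SE −0.473%; average (1.802+0.473+0.473)/3 = 0.92%.

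**4. All scenarios.** The visit-term column assumes three balanced light orders with nine completers each. With three lost subjects, the result is averaged over their orders.

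| Lost subjects | Nights each | SE reduction, no visit term | With visit term |
|---|---|---|---|
| 1 | 1 | 0.1–0.3% | 0.1–0.3% |
| 1 | 2 | 0.9–1.0% | 0.9–1.0% |
| 3 | 1 | 0.2–0.9% | 0.2–0.9% |
| 3 | 2 | 2.7–2.9% | 2.6–2.8% |

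**5. What t-tests on available pairs already recover.** A two-night subject takes one pair from 27 to 28: 1.8% for that pair, 1.8/3 = 0.6% on average. The mixed model adds 0.92−0.60 to 1.00−0.60, that is 0.3–0.4 percentage points. A one-night subject adds nothing to a complete-case ANOVA or a paired t-test.

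**6. Baseline.** If the baseline is taken on each experimental night and has within-subject correlation r with the outcome, adjustment multiplies the SE by √(1−r²).
- r = 0.3: 1−√0.91 = 4.6%.
- r = 0.5: 1−√0.75 = 13.4%.
- Baseline taken only once: it is constant across a subject's nights and cancels from a within-subject contrast of completers, so the gain is zero.

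Both values of r are assumed. That the baseline recurs each night is inferred, because the Protocol describes one overnight stay.

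**The case against.** The strongest reply is that almost nothing turns on this. Losses are expected to be few, and a schedule failure can be rescheduled. A subject removed at the one laboratory entry that the documents describe has no experimental night to lose. That the checks recur before later visits is inferred. Replacement together with repeated-measures ANOVA points naturally to 27 completers, and nothing in the SAP suggests that the t-tests would use other subjects. The calculation treats variances as known, which slightly flatters the mixed model. The baseline is a separate matter from replacement, and its larger figures should not lend weight to the smaller ones.

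Most of this stands. It limits the point to a small gain in efficiency and a missing statement of the analysis set. It does not remove the point: drop-out after a completed night is possible on the three-night reading, and a complete-case default is a choice that the SAP leaves unwritten. The baseline gain is shown separately for that reason. It concerns mainly gait, since the EEG outcome is already expressed as a change.

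Two stronger readings are tempting, and neither is supported. A reader might infer that replacing randomised subjects biases the light comparisons. Removal before the first experimental night cannot bias a within-subject contrast. Later removal would do so only if it depended on the response to an earlier light, which the documents do not suggest. A reader might also take the roughly 20% failure rate in Study Procedures as attrition. It refers to the screening visit, before randomisation, and says nothing about later loss.

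**Conclusion.** The point holds as a minor one. Under the three-night reading, the named ANOVA would ordinarily set aside completed nights of replaced subjects, and the pairwise tests could rest on a different set. The documents do not say outright that those nights are discarded.

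The cost in precision is about 0.1–1.0% of the SE for one lost subject and 0.2–2.9% for three, on assumed loss counts and SDs. The possible gain from the baseline is larger, 4.6% or 13.4%, but depends on an assumed correlation and on a baseline taken every night. No bias is claimed.

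**What to change.** In the SAP, replace the analysis sentence with text such as:

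*Each primary outcome will be analysed with a linear mixed model (subject random; light condition and visit fixed; the same-night pre-sleep baseline as covariate where the outcome is not already a change from it), including every randomised subject with at least one tested night. Pairwise light comparisons are taken from this model. A replacement is added and does not displace the nights of the subject replaced.*

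If the baseline is taken only once, the covariate can be left out.

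Also report the numbers removed and replaced, by visit and light order. The Protocol already provides for "indicating in the medical record that the subject was dispaneled for cause", so these counts need no drug or alcohol results.

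The cost is a slightly unbalanced analysed set, a few degrees of freedom for the visit and baseline terms, and a little more analysis work. No trial procedure changes.

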Title of Study: Toileting at Night in Older Adults: Light to Maximize Balance, Minimize Insomnia

NCT number: NCT01350505

Date of document: 9/26/18

Initial analysis plan

To test our Primary Hypothesis that a long wavelength light stimulus delivered at night will improve gait and not change alertness, we will examine stride-to-stride variability in speed and change in EEG delta power as our two primary outcome measures. Statistical significance will be determined with independent repeated measure analyses of variance (ANOVA) with *post hoc t*-tests. Our *a priori* hypothesis is that gait will be progressively improved such that dim light < orange light = room light and that alertness will be improved such that dim light = orange light < room light.

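### The allocation wording does not fit the three-visit design, and on that design the SAP specifies no visit term, which can cost precision

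*Protocol*

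**What the plan says.** On allocation, the Protocol (Study Procedures) says "Subjects will be block randomized in three groups of nine (three in each condition), with drop-outs replaced", and also that "subjects who are disempaneled will be replaced". Neither statement mentions an order of lights.

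The number of visits appears only in the last paragraph of the Protocol, which recruits for a later extra night from "subjects who completed all three of the visits previously described".

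On testing, the evening baseline sequence includes two walkway tests, followed by "a five minute break while seated, and the sequence repeated". Of this baseline the Protocol says: "This will serve as a baseline test to account for interindividual variability". At the night awakening, "Subjects will be tested with the same sequence as at baseline".

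On analysis, the SAP (Initial analysis plan) says "Statistical significance will be determined with independent repeated measure analyses of variance (ANOVA"), followed by post hoc t-tests. It lists no model terms. One primary outcome, EEG delta power, is described as a change, without saying from what. The other, stride-to-stride variability in speed, is not described as a change.

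**The concern.** Taken literally, three subjects per condition in each block of nine is a parallel-group allocation. Three completed visits and a repeated measures ANOVA point instead to every subject receiving all three lights on separate nights. A reader cannot tell from the text what is randomised: a light, a starting light, or an order of lights.

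On the three-visit reading, subjects repeat the same walkway, vigilance and EEG tests many times, so results could drift from visit to visit through practice or familiarity with the laboratory. If the analysis has no term for visit, that drift goes into the residual. At stake is precision. The SAP predicts that some pairs of lights are equal (orange and room light for gait, dim and orange light for alertness), and such predictions are better supported by narrow confidence intervals than by a non-significant test with wide ones.

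**Working it through.** **Step 1. Block structure.** 3 subjects × 3 conditions = 9 per block, and 3 blocks × 9 = 27. The Protocol's figures agree with each other. Nine subjects cannot be spread evenly over all six possible orders (9/6 = 1.5), but they fit three orders exactly (9/3 = 3). The block size is therefore compatible with a balanced-order design, although the text does not describe one.

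**Step 2. Amount of repetition.** Walkway tests per evening: 2 per sequence × 2 passes = 4. The night test adds 2 (one pass) or 4 (two passes). If the whole procedure recurs at each visit, the tests completed before the night test are:
- visit 1: 4
- visit 2: 4 + 2 + 4 = 10, up to 4 + 4 + 4 = 12
- visit 3: 10 + 2 + 4 = 16, up to 12 + 4 + 4 = 20

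A shift across visits is plausible. Its size is not in the documents.

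**Step 3. Model for the illustration.** Outcome = subject + light + visit + error, with total SD 1. Inputs:
- N = 27, from Step 1
- correlation between nights ρ = 0.5, so error variance 1 − ρ = 0.5 (assumed)
- visit effects −s/2, 0, +s/2, with s = 0.25, 0.5 or 1.0 SD remaining after any baseline adjustment (assumed)
- two-sided 5% test (assumed)
- light effects 0, d, d with d = 0.533 SD, chosen to give about 80% power
- each light equally frequent at each visit

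Noncentrality: λ = 27 × (2/3) × d² / (1 − ρ) = 27 × 0.667 × 0.284 / 0.5 ≈ 10.2. With no visit effect, power is about 80% on F(2,52). It is about 0.1 points lower on F(2,50), which is the model with a visit term.

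**Step 4. What omitting visit does.** With g² = (s/2)²/(1 − ρ), the visit shift adds 54g² to the scaled error sum of squares on 52 df. The expected error mean square is therefore inflated by (52 + 54g²)/52. The 95% CI half-width of a pairwise contrast is t × √[2(1 − ρ) × ratio / 27], with t = 2.007 on 52 df. With visit fitted, t = 2.009 on 50 df and the ratio is 1.

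| Shift s (SD) | 54g² | Variance ratio | Half-width, no visit term | Power, no visit term | Type I error, no visit term |
|---|---|---|---|---|---|
| 0.25 | 1.69 | 1.03 | 0.392 | 79% | 4.6% |
| 0.5 | 6.75 | 1.13 | 0.410 | 75% | 3.5% |
| 1.0 | 27.0 | 1.52 | 0.476 | 60% | 1.1% |

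With visit fitted, the half-width is 0.387 SD, power 80% and type I error 5% at every shift. Power and type I error were obtained by simulation.

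**Step 5. Sensitivity to the correlation.** At a 0.5 SD shift, with the effect rescaled to keep 80% power when visit is fitted, power without the term is 77% at ρ = 0.3 and 68% at ρ = 0.8.

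**Step 6. Other randomised orders, no visit term, shifts 0.25/0.5/1.0 SD.** Type I error is 4.7%, 3.9% and 1.9% if the starting light is balanced and the other two are random. It is 5.0%, 5.0% and 5.1% if order is unrestricted. Validity holds under every randomised scheme examined.

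**The case against.** The strongest reply is that the three-visit design is itself an inference. The allocation sentence reads as parallel groups, and a repeated measures ANOVA could also describe baseline and night data in parallel groups, where order and visit would not arise. That stands as a reason to reconcile the text first. It leaves the reference to three completed visits unexplained, so the three-visit reading is the more likely one.

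Second, a reader might infer that the SAP rules out a visit term. It does not. It lists no terms at all, not even light, so the term is unspecified rather than excluded.

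Third, a reader might infer that the tests have inflated type I error. If the starting light were balanced and the other two always followed in the listed order, type I error without a visit term would be 5.9%, 8.3% and 15.2% at the three shifts. The documents describe no such systematic order. They say subjects are randomised, so these figures do not characterise this trial.

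Fourth, the loss is small unless the shift is large: about one point of power at 0.25 SD. Four baseline walks precede even the first night test, and a change from the same evening's baseline would cancel any shift common to both. This also stands, with the limit that the stated purpose of the baseline is variability between subjects, and the SAP does not say that it enters the gait analysis.

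Finally, a visit term does not turn a predicted equality into a tested one. That is correct: it only narrows the interval.

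**Conclusion.** The point holds as a cheap improvement. The allocation wording and the three-visit wording conflict and need reconciling. If each subject receives all three lights, naming visit number in the model is a better analysis than the ANOVA as written. The benefit is precision, and it runs from negligible (79% against 80% power at a 0.25 SD shift) to substantial (60% against 80% at 1.0 SD). These sizes rest on the assumed correlation, effect and shifts, with only N = 27 derived from the Protocol. They would be smaller if a same-evening baseline absorbed part of the shift. The documents do not support a claim of bias or of excess false positives: with randomised order the ANOVA is unbiased on average, and with balanced order it is conservative.

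**What to change.** **SAP, Initial analysis plan.** Analyse each primary outcome with a model containing subject, light and visit number, and take the post hoc contrasts with 95% CIs from that model.

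**Protocol, Study Procedures.** Replace the allocation wording with a statement that each subject is randomised to an order of the three lights, that within each block of nine every light occurs equally often at each visit (three times), and that a replacement takes the dropped subject's order.

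A single three-order Latin square (ABC, BCA, CAB) achieves this balance, but each light then always follows the same other light, so any carryover is confounded with light. Alternating it between blocks with the other square (ACB, CBA, BAC) avoids that. With three blocks the split is two to one (18 and 9 subjects), so predecessors are mixed but not equally frequent.

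If allocation is already complete, report the orders used and still fit visit number.

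**Cost.** One sentence in each document, a randomisation list or a table of orders used, and 2 error df (52 to 50). If there is no visit effect, that costs about 0.1 points of power. No extra subjects or visits are needed.

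### Does permitting an LED in place of the filtered lamp leave the orange condition too loosely defined for the primary analysis?

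*Protocol*

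**What the plan says.** The Protocol (Study Procedures, the paragraph on the experimental light) introduces the white lights in lux: "The first two conditions, very dim white light (0.5 lux, low mesopic range) and dim white room light (5 lux"). It then says: "The orange light condition will be produced by filtering the fluorescent lamps with an acrylic filter", names the filter product, and sets the output: "so as to produce 1×10^{13} photons" per cm² per second, "or an equivalent LED light". The LED gets no peak wavelength, bandwidth or tolerance of its own. The one stated measurement check concerns illuminance and comes before the orange sentence. Nothing says whether the source stays the same across subjects, or that it is recorded at each session.

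On design, the Protocol says: "Subjects will be block randomized in three groups of nine (three in each condition), with drop-outs replaced". The follow-up paragraph implies that each subject makes three visits, so each has one orange session.

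The SAP (Initial analysis plan) says: "Statistical significance will be determined with independent repeated measure analyses of variance (ANOVA"), followed by post hoc t-tests. Orange is one level for both primary outcomes. Gait under orange is predicted to exceed dim and equal room light; alertness under orange is predicted to equal dim and fall below room light. There is no source factor.

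**The concern.** Orange is the condition on which the Primary Hypothesis turns, and the text permits two physical ways of making it without defining equivalence. The white lights are specified in lux and the orange light in photons, so an LED could be matched on either scale. Even when matched on photons, its spectrum stays open.

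The scale matters because subjects are tested in dim light after two hours of darkness: "After 2 hours in darkness subjects, will be awakened by the technician". Rod vision may contribute there, and rod sensitivity falls steeply across the orange part of the spectrum. Two lights with the same photon count could therefore act differently.

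If some subjects had the lamp and others an unlike LED, the pooled orange mean would be a blend. Both hypotheses predict an equality involving orange (with room light for gait, with dim light for alertness). A blend could make either prediction look met or missed, and a small trial would be unlikely to reveal it.

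**Working it through.** The documents give no power calculation, spectrum or effect size, so there is no planned figure to reproduce. Everything below except the photon flux, the lux levels and the group sizes is an assumption.

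**1. Does the stated flux fix the stimulus?** The flux is 1×10^13 photons/cm²/s = 1×10^17 photons/m²/s. For light of a single wavelength λ:

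- irradiance E = 10^17 × hc/λ
- illuminance = 683 × V(λ) × E, with standard photopic V assumed

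| λ | E (W/m²) | V | Lux |
|---|---|---|---|
| 590 nm | 0.03367 | 0.757 | 17.4 |
| 620 nm | 0.03204 | 0.381 | 8.3 |

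The ratio is 17.4/8.3 ≈ 2.1. With rod weighting (1700 × V′ × E), the values are 3.75 and 0.40, a ratio of about 9.3. The two white lights differ by 5/0.5 = 10. So photon flux alone does not determine the light.

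**2. Is that the contrast the Protocol permits?** No. The permitted alternatives are one named lamp-and-filter combination and an LED equivalent to it, not two LEDs of different colour. For lamp against LED at equal photons, the rod-weighted ratio depends on the assumed filter edge and LED peak:

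| Assumed filter edge | Assumed LED peak | LED/lamp, rod-weighted |
|---|---|---|
| 570–610 nm, all combinations | 590–620 nm | 0.10–9.98 |
| 590 nm (mid-range) | 590–620 nm | about 0.34–3.7 |
| 590 nm (mid-range) | 600–610 nm | about 0.7–1.9 |

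The near-tenfold values arise only from pairing opposite extremes (a 610 nm edge with a 590 nm LED, or a 570 nm edge with a 620 nm LED). Such a pair is hard to call equivalent.

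**3. What would a mix do to the analysis?** Let f be the share of orange sessions on the LED and d the source difference, in SD units of the paired contrast. The contrast shifts by f×d and its variance becomes 1 + f(1−f)d². Take n = 27 (three groups of nine, summed), two-sided 5% and a true contrast of 0.5 SD:

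- One source: Φ(0.5×√27 − 1.96) = Φ(0.638) = 73.8% power.
- f = 0.5, d = 0.5, variance effect only: SD = √1.0625 = 1.031, power 71.2%.
- Same f and d, including the shift: contrast 0.50 − 0.25 = 0.25, power 24.2%.
- d = 0: no loss.

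The shift matters far more than the added noise, and it requires both f > 0 and d ≠ 0.

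**4. Would a source term help?** Each subject has one orange session, so source varies between subjects. If one group of nine used the LED:

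- SE of the source difference = √(1/9 + 1/18) = 0.408 SD
- SE of the pooled contrast = 1/√27 = 0.192 SD

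The source term is therefore about 2.1 times less precise than the main comparison. Let D = 0.56 SD be the paired difference detectable with 80% power. Suppose the source gap is 0.32 D to 0.97 D (log10 of 2.1 and 9.3, assuming an outcome linear in log light in which one log unit is worth D). By simulation the source term then detects it in 7% to 25% of trials. If the lamp truly equals room light, the pooled orange-versus-room test rejects in 6% to 13% of trials, against 5% with no mix.

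**The case for a change.** The strongest case for acting is that the SAP's analysis would rarely expose a mix, so the only real protection is a definition of equivalence and a rule to keep one source. Both are cheap: a measurement per source and one recorded field. Two lights could meet the flux figure and still differ in their effect on a dark-adapted eye. Even with one source throughout, a reader of the plan cannot tell which light was meant, and that hampers replication.

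Part of this stands. The flux is not expressly applied to the LED, no spectrum or tolerance is given, and the calculation shows that flux alone leaves the spectrum open.

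The step to a threatened primary analysis does not stand. It needs both sources to be used within the study, the two to be materially unlike despite the requirement of equivalence, and the outcome to respond to the difference. The documents establish none of these. It is also not the case that nothing is given to match: a named filter and a photon flux stand in the same sentence as the LED option.

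Making source a factor and demoting the pooled orange result would replace the main comparison with subgroups of about 9 and 18. If the source changed between randomisation blocks, source would also be confounded with block and calendar time. Concurrent dim and room sessions would remove a drift shared by all lights, but not a difference between cohorts in the orange contrast itself.

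**Conclusion.** No change to the plan is needed. The Protocol and SAP do not conflict: one orange level is the right analysis when one source is used, and offering an LED as an equivalent reads most naturally as latitude in choosing apparatus. What remains is a minor gap in specification. A laboratory that controls and measures its lighting would be expected to match the substitute to the named filtered lamp, keep it, and describe it when reporting.

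With one source, or with two that act alike, the effect on the primary comparison is nil. It could be material only with an unlike mix, for example power falling from 73.8% to 24.2% when half the sessions are on a source differing by 0.5 SD. That figure rests on an assumed effect, mix and source gap, and nothing in the documents suggests such a mix. The one available change to the analysis would have 7% to 25% power in the illustration and would weaken the main comparison, so it offers no gain.

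The conclusion rests on reading the LED option as a choice of equipment and on one orange session per subject. Evidence that sources were in fact mixed would reopen the question.
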